### **Recruitment and randomization**

Patients who had visited or will visit LAUMC-RH with a diagnosis of ET on their records would be contacted and those interested in participating in the trial would be randomly assigned into either (1) cathodal tDCS or (2) sham tDCS.

One researcher who will not be blinded to group assignment will perform cathodal tDCS or sham tDCS. However, another researcher who will assess the outcome measures will be blinded to group assignment. The third blinded researcher will collect the demographic data

and assess adverse events. All participants will be blinded to the order in which the cathodal/sham conditions will be given.

## V. Study procedure

### Initial visit:

The first visit is an inclusion visit, where the examining physician takes a comprehensive history, performs a neurological exam, and verifies the inclusion/exclusion criteria. The physician will explain the protocol to the patient and provide him/her with information regarding the consent form, and the other questionnaires to be filled. The patient will be called within the following days to check if he/she agrees to participate in the research and therefore plan for the stimulation session.

### tDCS sessions:

Prior to starting the first tDCS session, the patient will be asked to fill his/her first TRG essential tremor assessment (TETRAS) scale which includes an activity of daily living subscale and a performance subscale (Elble et al. 2012).

The physician will then quantitatively analyze the tremor on the most affected side using an accelerometer. Two measures are obtained with the accelerometer: the tremor frequency and amplitude. Sensors are fixed on the skin at a given landmark (index finger) (Grimaldi and Manto 2010). The tremor will be assessed in two different positions: (1) at rest and (2) postural.

Subsequently TMS of the motor cortex contralateral to the hand used above will be performed with a figure-of-eight coil (70 mm) on a Magstim machine. To determine the optimal site of stimulation (hotspot), the coil will be moved around the primary motor cortex (M1) eliciting the largest MEP motor-evoked potentials (MEPs) from the first dorsal interosseous (FDI) of the hand tested above.

[figure not shown]
Finally, cathodal tDCS will be administered through a pair of conductive rubber electrodes covered by saline soaked sponges (35 cm^2). The current will be delivered continuously at 2 mA for 30 min through a battery-driven constant-current stimulator. The cathode will be positioned on the area representing the primary motor cortex and the anode over the contralateral supraorbital area.

tDCS stimulation (cathodal and sham) will be done daily for 5 consecutive days during weeks 1 and 5. Each stimulation session will last 30 minutes. tDCS will be performed while the patient is at rest, without any concurrent cognitive or motor task. The two tDCS sessions will be separated by a 23 day washout period.

### **Post tDCS/Clinical evaluation**

Patient will be asked to fill out their TETRAS at days 1 and 5 of each tDCS session (cathodal and sham), and days 12 and 19 after each tDCS session (cathodal and sham). Please refer to figure 1.

Accelerometer assessment of the tremor will be performed at days 1 and 5 of each tDCS stimulation session (cathodal and sham).

**Figure 1:** Study design and procedure

## **VI. Statistical Analysis**

The analysis will be conducted using the R statistical package. Demographic data will be summarized using frequencies, means, standard deviations and confidence intervals. The change in the TETRAS and Accelerometer scores will be assessed using Wilcoxon paired test at different time points (illustrated in figure 1) and the correlation between the TETRAS and Accelerometer scores will be tested using the Pearson method.

## **VII. Data Management**

The study records will be kept as confidential as possible. We will protect carefully the information about the patient. What we learn from samples will be described only in a way that does not identify the patient. To protect the patients' privacy, samples will be linked to a secret code. Names will only be recorded on the informed consent form. We will keep the secret code in a locked and carefully protected file, with access only granted to the principal investigator of the study and authorized personnel. The records will be monitored and may be audited without violating confidentiality. Published data resulting from the study will not mention the names of the people who participated in this study. The data will be published in peer-reviewed journals. Following the study, the data will be safely stored and kept for quality assurance.

## **VIII. Adverse Event Reporting**

The minor adverse events reported in association with use of tDCS (sensation of itching under the electrodes, mild skin erythema and headaches) will be provided the necessary short-term medical care by the investigator. They usually resolve spontaneously after stimulation is halted.

## **IX. Patients' withdrawal:**

No available conditions in the study protocol can trigger the patient's withdrawal. However, the patient can withdraw consent, at any point during the study, without any consequences.

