#### **Participants**

We will recruit 40 Patients diagnosed with essential tremor based on the 2017 movement society criteria (Bhatia et al. 2018)

Inclusion Criteria	Exclusion Criteria

• Patients who fulfil the 2017 Movement society concusses statement criteria for essential tremor

• Age 18 and above

	

• Isolated focal tremor (voice, head)

• Orthostatic tremor with a frequency of more than 12 Hz

• Task and position specific tremor

• Sudden onset and stepwise deterioration of tremor

• History of substance abuse or dependence in the past

	
 
• Comorbid medical conditions and medications capable of producing or enhancing tremors
 
• History of neurological disorders, brain tumors, brain surgery or abnormal neurological examination
 
• Epileptic disorders
 
• Cardiac pacemakers
 
• Metallic hardware in the head or scalp (surgical clips)
 
• Eczema or skin abrasion at the intended site of stimulation
 
• Currently pregnant or plan for pregnancy in the next 6 months
 
• Patients with prior experience with tDCS
 
• Major psychosocial problems or medical problems rendering informed consent impossible
 

--	---

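### The withdrawal section says no protocol condition can trigger withdrawal, and no other visible text says when to stop stimulation if an exclusion condition arises after entry

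*Protocol*

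**What the plan says.** Section IX (Patients' withdrawal) states: "No available conditions in the study protocol can trigger the patient's withdrawal". It then adds that a patient may withdraw consent at any time.

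Eligibility is checked at the inclusion visit (section V, Initial visit), where the physician "performs a neurological exam, and verifies the inclusion/exclusion criteria". Stimulation is arranged afterwards: "The patient will be called within the following days to check if he/she agrees to participate in the research".

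The schedule is in section V, tDCS sessions: "tDCS stimulation (cathodal and sham) will be done daily for 5 consecutive days during weeks 1 and 5", and "The two tDCS sessions will be separated by a 23 day washout period". In the cathodal condition, "The current will be delivered continuously at 2 mA for 30 min through a battery-driven constant-current stimulator".

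The exclusion criteria (section IV, Participants) include "Eczema or skin abrasion at the intended site of stimulation" and "Currently pregnant or plan for pregnancy in the next 6 months", as well as epileptic disorders, cardiac pacemakers and metal in the head or scalp.

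**The concern.** By listing these exclusions, the sponsor has decided that such patients should not enter the trial. A patient can meet one of them after entry, either between the inclusion visit and the first session or during the five weeks of stimulation. At that point the protocol gives the investigator no written ground for stopping, and the section where one would look says that no such condition exists.

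What is at stake is patient safety and consistent handling between patients. This is not a detail to be left to a statistical analysis plan: withdrawal criteria belong in the protocol, and this protocol has a section on them.

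**Working it through.** **Timing (section V, tDCS sessions).**
- Block 1: 5 consecutive days in week 1 = days 1 to 5.
- Washout: 23 days = days 6 to 28 (5 + 23 = 28).
- Block 2: starts on day 28 + 1 = 29 and runs to day 33.
- Cross-check: the first day of week 5 is 4 × 7 + 1 = 29, so the week numbers and the washout length agree.

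**Gap since the stated check.** The inclusion visit precedes day 1. Block 2 therefore falls at least 29 − 1 = 28 days (first session) to 33 − 1 = 32 days (last session) after it. For a patient given sham first, all active stimulation lies in that window: 5 × 30 min = 150 min at 2 mA. For a patient given cathodal first, the active sessions are days 1 to 5 and block 2 is sham.

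**Which exclusions can newly arise.**
- Skin lesion at the site: yes. The protocol itself lists mild erythema as a known effect of tDCS.
- Pregnancy: an unplanned one, yes. A planned one is already covered, because the criterion looks 6 months ahead. The last scheduled TETRAS is on day 29 + 18 = 47 if day 19 is counted from the start of block 2, or on day 33 + 19 = 52 if counted from its end. Both are well inside 6 months.
- Epileptic disorder, pacemaker, metal in the head or scalp: possible.

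**Does any other section supply a stopping criterion?**

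| Protocol section | What it provides | Criterion for stopping? |
|---|---|---|
| IV, Recruitment and randomization | A blinded researcher assesses adverse events | No |
| V, tDCS sessions and Post tDCS | TETRAS, accelerometry, TMS localisation, stimulation | No; no re-check stated in the text |
| VIII, Adverse Event Reporting | Short-term care of minor events, which usually resolve once stimulation stops | No |
| IX, Patients' withdrawal | No triggering condition; consent may be withdrawn | No |
| X, Quality assurance, monitoring & safety | Saline-soaked sponges against skin irritation; AE recording, including action taken; prompt notice of SAEs to the principal investigator; no external committee | No |

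The protocol provides for detection and care. It does not provide the next step, a stated reason to stop.

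**The case against.** The strongest reply is that section IX concerns leaving the study and does not mention stimulation. A session can be skipped or ended without withdrawing the patient. The sentence can also be read as descriptive, meaning only that no criteria were predefined. A reader might infer that the protocol forbids the investigator to stop; the text does not establish that. The recording of action taken in section X, and the reference in section VIII to events resolving once stimulation stops, both leave room for ad hoc stopping. This part of the objection stands. It narrows the point without removing it, because under either reading no visible section ties a new contraindication to a decision.

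A reader might also infer that nobody looks at the patient again before block 2. That would be an argument from silence. Figure 1 is not shown and may include a re-check, staff place electrodes at every session, and adverse events are assessed by a dedicated researcher. Even a re-check drawn in Figure 1 would leave a failed check without a stated consequence in section IX.

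Finally, stopping rules have a price. Mild erythema is expected and should not end treatment. The person giving stimulation is unblinded, and the paired Wilcoxon comparison in section VI can lose a pair for each incomplete period. These are reasons to draft the criteria narrowly.

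**Conclusion.** The point holds as an inexpensive safety improvement. Section IX affirmatively says that no condition triggers withdrawal, and no other visible text gives a criterion for stopping stimulation, although several listed exclusions can arise before or during block 2 on days 29 to 33. The stated rule attaches no consequence to a new contraindication.

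It would be tempting to put the size at the whole sham-first sequence, for example 20 of 40 patients under equal allocation. The documents do not support that. The figure would only count patients who receive active stimulation in block 2, the allocation ratio is not stated, and no rate of new contraindications is given. The number affected is therefore not estimated, and no effect on the efficacy estimate is claimed.

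The conclusion rests on the visible text and on the inclusion visit preceding day 1. Figure 1 could change the re-check element, but a re-check alone would not supply the missing consequence.

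**What to change.** Replace the first sentence of section IX with wording such as:

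*Stimulation (cathodal or sham) will be discontinued if any of these arises: eczema or an abrasion at the stimulation site; pregnancy; a seizure or epileptic disorder; a cardiac pacemaker; metal implanted in the head or scalp; or an SAE judged related to stimulation. Discontinued patients stay in follow-up if they agree.*

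Naming the items avoids having to decide later which exclusions count as safety contraindications, and an abrasion or eczema is distinct from the mild erythema that is expected. Confirm the items at the existing visit on day 1 of each block, unless Figure 1 already does so, and look at the skin whenever electrodes are placed. Apply the same criterion in both conditions, with the decision made by the investigator.

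**Cost.** One replaced sentence, 2 confirmations per patient (2 × 40 = 80) and 2 × 5 = 10 skin checks per patient (10 × 40 = 400), all at existing visits with existing staff.

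**Downsides.** A few patients may contribute an incomplete period, against a margin of 40 − 36 = 4 over the stated requirement. The unblinded operator could prompt stopping more often under cathodal than under sham; the common criterion and the investigator's decision limit this but do not remove it.

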## **X. Quality assurance, monitoring & safety**

No external committees will be overseeing the study. No interim analysis will be done. To prevent skin irritation, sponge electrodes will be soaked in saline water.

The investigator is responsible/in charge of recording and reporting all the adverse events and serious adverse events (SAEs) that might happen throughout the entire research protocol, from the time of taking consent, and throughout the whole period required to monitor the participants. SAEs will be recorded on a comprehensive form provided for this purpose. This form will be completed, printed, dated, signed, and the principal investigator will be promptly notified. Moreover, regardless of the time of onset following the protocol, all SAEs suspected to be the result of the research protocol should be reported to the investigator unless other reasonable explanation exists. All the other adverse events (AEs) will be reported only on the medical file of each patient, including the date of onset, characteristics, intensity, and duration, etiologies, taken actions, treatments, and resolutions if any. There are no specific safety measures related to this research and no important safety data to be collected.

## **XI. Dissemination of Results and Publication policy**

The data will be published in peer-reviewed journals. If the results show a significant improvement in essential tremor patients, further studies will be designed to study the optimal maintenance tDCS dose and the long term effect of tDCS.

